## **4.4** RANDOMIZATION AND BLINDING

Up to a total of 40 subjects will be randomized at a 3:2 ratio to Group 1 (CAM2038 q1w) or Group 2 (CAM2038 q4w). Per Protocol Amendment 05, up to additional 16 subjects will be enrolled to Group 3 to receive 160 mg CAM2038 q4w. The study is not blinded.

At least 20 subjects, and up to 24 subjects, will be randomized to Group 1 and assigned to 1 of the following 4 injection site sequences at a 1:1:1:1 ratio: ABDC, BCAD, CDBA, and DACB, where A=buttock (reference), B=abdomen, C=thigh, and D=back of upper arm. For Group 2 (CAM2038 q4w), approximately 16 subjects will be enrolled.

## 5.0 ANALYSIS POPULATIONS

## 5.1 SAFETY POPULATION

The safety population will include all subjects who have received study medication. Analyses based on this population will group subjects according to the treatment they actually received regardless of the treatment they are randomized to receive. All safety analyses will use the safety population.

#### **5.2** PHARMACOKINETIC POPULATION

Pharmacokinetic (PK) population will consist of all subjects in the Safety population who have provided PK data.

#### **5.3** EVALUABLE PHARMACOKINETIC POPULATION

Evaluable pharmacokinetic (PKEVAL) population will consist of all subjects in the PK population who have provided sufficient PK data for all 4 randomized injection sites to derive PK parameters of interested (Group 1), or have provided PK data after the last injections of CAM2038 q4w (Groups 2 and 3). All primary PK summaries will be based on the PKEVAL population.

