# 12 STATISTICAL METHODS AND DETERMINATION OF SAMPLE SIZE

### 12.1 Statistical and Analytical Plans

Complete details of the statistical analyses to be performed will be documented in a SAP. The SAP may include more detail of analysis populations, summary strategies, and any clarifications or changes necessary due to, for example, regulatory requests. The SAP must be finalized before database lock. Any changes to the final SAP will be discussed in the final study report.

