### **12.2 Analysis Populations**

Three study populations are defined.

- Safety population: All subjects who receive at least part of an injection of the study medications. All safety analyses will be based on the Safety population.
- **Pharmacokinetic population**: The PK population will consist of all subjects in the Safety population who have provided sufficient PK data for all 4 randomized injection sites to derive PK parameters of interest (Group 1), or have provided PK data after the last injection of CAM2038 q4w (Group 2 and Group 3). All PK summaries will be based on the PK population.
- Efficacy population: The efficacy population will be the intent to treat population consisting of all subjects that have received at least 1 injection of CAM2038 and provided some efficacy measures.

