#### 12.3.5 Missing data

Missing dates/times in AE and concomitant medication data and other missing safety data will be handled as described in the SAP. There will be no imputation schemes applied to missing PK data.

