## **10.3** ANALYSIS OF PHARMACOKINETICS

Summaries of plasma concentrations of BPN and norBPN will be presented for the PKEVAL population and PK population by group and injection site, if applicable. The following descriptive statistics will be presented at each nominal time point: n, arithmetic mean, standard deviation, and coefficient of variation percentage (CV%), median, geometric mean, geometric CV%, minimum and maximum values. Mean plasma concentration-time data will be displayed for the PKEVAL population and the PK population in linear and semi-logarithmic scales by group and injection site, if applicable. Individual plasma concentrations of BPN and norBPN will be listed for the PK population by group.

The PK parameters (Section 10.1) will be listed for the PK population and summarized for the PKEVAL population and PK population by group and injection site, if applicable. Summary statistics will include n, arithmetic mean, standard deviation, CV%, median, geometric mean, geometric CV%, minimum and maximum values.

For Group 1 (CAM2038 50 mg/mL q1w), the following considerations will apply in the PK analyses. The primary PK parameters will be  $AUC_{ss}$  and  $C_{ss,max}$  after steady state injections of CAM2038 q1w at different injection sites. The injection site buttock will be the reference. The analyses will be based on log-transformed data. The natural log-transformed AUCss and Css,max data will be analyzed using an ANOVA model, sequence, subject within sequence (1, 2, 3, 4 corresponding to A/B/D/C, B/C/A/D, C/D/B/A, D/A/C/B, where A=buttock, B=abdomen C=thigh, or D=back of upper arm), period, and

treatment sites (treatment sites: A=buttock, B=abdomen C=thigh, or D=back of upper arm). The estimated injection site effects, injection site differences versus the reference (B-A, C-A, and D-A), and the 90% confidence intervals of the estimated differences will be presented. The above estimates will be expressed on the raw scale (expressed after performing the anti-log).

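### The SAP names no population for the Group 1 injection-site ANOVA; the likeliest reading, four-site completers only, drops usable data from subjects with two or three evaluable sites

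*SAP*

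**What the plan says.** SAP 5.3 defines PKEVAL for Group 1 as subjects in the PK population "who have provided sufficient PK data for all 4 randomized injection sites to derive PK parameters of interested (Group 1"), and adds "All primary PK summaries will be based on the PKEVAL population". The wider PK population in SAP 5.2 needs only that a Safety-population subject has provided PK data.

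SAP 10.3 states that the PK parameters are "summarized for the PKEVAL population and PK population by group and injection site, if applicable". The paragraph on the Group 1 ANOVA calls AUCss and Css,max the primary parameters and lists the model terms as "sequence, subject within sequence (1, 2, 3, 4 corresponding to A/B/D/C, B/C/A/D, C/D/B/A, D/A/C/B"), then period and site. It asks for 90% confidence intervals for each site against the buttock, and it names no population.

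Protocol 12.2 puts the four-site rule in its own PK population, for subjects "who have provided sufficient PK data for all 4 randomized injection sites to derive PK parameters of interest (Group 1"), and says "All PK summaries will be based on the PK population". On missing values, Protocol 12.3.5 says "There will be no imputation schemes applied to missing PK data".

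**The concern.** AUCss and Css,max are the primary parameters and primary PK summaries use PKEVAL, so the natural reading is that the ANOVA is fitted to four-site completers. Protocol 12.2 supports that reading, but it remains an inference. Because SAP 10.3 has just used both populations for the descriptive summaries, two analysts could fit the ANOVA to different sets.

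On the completer reading, one unusable profile removes a subject's other three from the ANOVA. The model does not require this. With a subject effect fitted, site differences are estimated within subject, and two evaluable sites are enough to contribute.

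The site ratios are the only modelled comparison under a primary objective, and they rest on 20 to 24 subjects. What is at stake is precision, and having the analysis set fixed before it is known who is incomplete.

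**Working it through.** **Inputs from the documents.** Group 1 has 20 to 24 subjects (SAP 9.5), allocated 1:1:1:1 to ABDC, BCAD, CDBA and DACB (SAP 4.4). The model is a log-scale ANOVA with sequence, subject within sequence, period and site, and 90% intervals for B-A, C-A and D-A (SAP 10.3). SAP 9.5 gives no power calculation, within-subject CV or dropout rate, so there is no planned precision figure to reproduce.

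**Assumptions.** The number of incomplete subjects is 1, 2 or 4. The within-subject CV is 20%, 30% or 40%; it affects the ratio-scale interval but not the relative width on the log scale.

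**Formulas.** The subject effects absorb sequence. Let v be the variance multiplier of a site contrast from least squares on subject, period and site.

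- Log half-width = t(0.95, df) × s × √v, with s = √ln(1 + CV²).
- df = profiles − subjects − 3 (periods) − 3 (sites).
- Interval factor = exp(half-width); the ratio is multiplied and divided by it.

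**Worked case.** One subject per sequence loses the last site and keeps three. At CV 30%, s = √ln(1.09) = 0.2936.

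| | N=24, completers | N=24, all with ≥2 sites | N=20, completers | N=20, all with ≥2 sites |
|---|---|---|---|---|
| Subjects | 20 | 24 | 16 | 20 |
| Profiles | 80 | 92 | 64 | 76 |
| df | 80−20−6 = 54 | 92−24−6 = 62 | 64−16−6 = 42 | 76−20−6 = 50 |
| v | 0.1000 | 0.0882 | 0.1250 | 0.1071 |
| t(0.95, df) | 1.6736 | 1.6698 | 1.6820 | 1.6759 |
| Half-width | 0.1554 | 0.1456 | 0.1746 | 0.1610 |
| Interval factor | 1.168 | 1.157 | 1.191 | 1.175 |

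Width ratio, completers over all: 0.1554/0.1456 = 1.067 at N=24, and 0.1746/0.1610 = 1.084 at N=20.

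**Other patterns of loss.** Affected subjects were drawn at random (1,000 draws) and the width averaged over the three contrasts. Width ratios for 1, 2 and 4 incomplete subjects:

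| Pattern | N=24 | N=20 |
|---|---|---|
| (a) one unusable profile, all injections given | 1.015, 1.032, 1.069 | 1.019, 1.040, 1.088 |
| (b) one missed injection, next profile also left out | 1.010, 1.020, 1.044 | 1.011, 1.025, 1.056 |
| (c) one missed injection, all later profiles left out | 1.006, 1.012, 1.026 | 1.007, 1.015, 1.034 |
| (d) last two sites lost | 1.008, 1.016, 1.035 | 1.009, 1.020, 1.044 |

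If the last three sites are lost, the ratio is 1.000, because a single site carries no within-subject contrast.

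**On the ratio scale, 4 incomplete subjects.**

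- CV 30%, N=24: factor 1.169 on the four-site set, against 1.157 (a), 1.161 (b), 1.164 (c) and 1.163 (d).
- CV 30%, N=20: 1.192 against 1.175, 1.181, 1.185 and 1.183.
- CV 20%, N=24: 1.111 against 1.103 to 1.108.
- CV 40%, N=24: 1.227 against 1.211 to 1.221.

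The four-site factors differ in the third decimal from the worked case because random draws do not stay balanced over sequences.

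**An average, not a certainty.** With simulated residuals and an estimated residual SD (2,000 datasets, 4 incomplete), the four-site interval was the wider one in 95%, 91%, 81% and 89% of datasets for (a) to (d) at N=24, and in 94%, 90%, 81% and 89% at N=20.

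**The case against.** The strongest reply is that the four-site rule is a deliberate, pre-specified choice, stated consistently in the Protocol and the SAP, and that analysing completers of a four-period crossover is legitimate. The harm needs two conditions: the ANOVA must be restricted to PKEVAL, and some subjects must finish with exactly two or three evaluable sites. The effect is small, and no margin or power target turns on it. Incomplete subjects are still listed and descriptively summarized in the SAP's PK population. Replacement subjects are allowed. Protocol 12.1 does say "The SAP may include more detail of analysis populations, summary strategies, and any clarifications or changes necessary due to" matters such as regulatory requests, which need not cover replacing the Protocol's PK population. And weekly periods without washout mean that partial subjects cannot be included without a new exclusion rule.

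Much of this stands and limits the point. The data are lost to the ANOVA only, the size is conditional and modest, and the change is a departure that must be declared. The rest does not remove the point. Consistent wording does not make the rule efficient for a model that can use partial subjects. If the wider population was intended, the SAP still has to say so. Replacement is discretionary, closes once Groups 1 and 2 are analysed (SAP 9.3 and 10.3), and restores numbers without recovering the dropped profiles. An exclusion rule is needed in any case, because SAP 5.3 does not define what counts as sufficient data.

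**Conclusion.** The point holds. The four-site set is the best-supported reading for the Group 1 ANOVA, and on that reading within-subject information from subjects with two or three evaluable sites is left out. The cost is an interval on average about 3% to 9% wider on the log scale with 4 incomplete subjects, and about 0.6% to 4% wider with 1 or 2. It is zero if nobody is incomplete or if incomplete subjects have only one site.

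These sizes rest on assumed counts and patterns of missing profiles, and the ratio-scale factors also on an assumed CV. They concern precision only; bias from selective dropout was not assessed. No conclusion rule changes. It is a cheap improvement worth making, not a flaw that undermines the study.

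**What to change.** In SAP 10.3:

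1. State that the primary Group 1 ANOVA is fitted separately to ln AUCss and ln Css,max, using every site-period in which that parameter can be estimated, in subjects with at least two evaluable sites.
2. State before database lock which profiles are left out of the steady-state analysis after a missed or late injection, because the weekly periods follow one another without washout.
3. Keep the four-site PKEVAL fit as a sensitivity analysis.
4. Declare the departure from Protocol 12.2 and the reason for it.

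The cost is SAP text, one exclusion rule and a declared departure; no new data are needed. The number of subjects will differ by site and the data will be slightly unbalanced. If the sponsor prefers to keep completers as the primary set, SAP 10.3 should at least name that set for the ANOVA and add the all-evaluable fit as the sensitivity analysis.

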#### **5.4** INTENT-TO-TREAT POPULATION

The efficacy population will be the intent-to-treat population consisting of all subjects that have received at least 1 injection of CAM2038 and provided some efficacy measures. All efficacy summaries will be based on the ITT population.

## 6.0 GENERAL CONVENTIONS

Unless otherwise stated, all statistical analyses will be performed using SAS Version 9.2 and all hypothesis tests will be conducted at a two-sided significance level of 0.05. P-values will be presented with 3 decimals and p-values that are less than 0.001 will be presented as <0.001.

Continuous (non survival related) data will be summarized using descriptive statistics: number of observations (n), mean, standard deviation (SD), median, minimum, and maximum. Frequencies and percentages will be used to summarize categorical (discrete) data. Presentations of categorical data will generally suppress percentages for items where the count is zero in order to draw attention to the nonzero counts. In general, mean, standard deviation, median, minimum, maximum, and percentages will be presented with one decimal.

Unless otherwise stated, confidence intervals, when presented, will be constructed at the two-sided 95% level. For binomial variables, the 95% confidence intervals will be constructed using the exact method.

Data listings will present all data collected on CRFs by study drug, center, and subject number. Unless otherwise stated data will be presented by treatment and overall.

## 6.1 DEFINITION OF BASELINE

Unless otherwise stated, the last observed measurement on the date of randomization will be considered the baseline measurement. If multiple observations are made during baseline, the baseline will be defined as average of the observations obtained during the baseline phase.

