## 9.3 Method of Assigning Subjects to Treatment Groups

Subjects who have provided written informed consent will be assigned a unique number in the screening process. This number will be used to identify the subject throughout the study. Once any subject number or randomization number is assigned, it cannot be reassigned to any other subject.

On Day 1, before the first dose of CAM2038, subjects will be randomized into Group 1 (CAM2038 q1w) or Group 2 (128 mg CAM2038 q4w) in a 3:2 ratio, or enrolled into the additional Group 3 (160 mg CAM2038 q4w).

For subjects in Group 1, injection site rotation will be randomized (on Day 1) to avoid bias in the assignment of injection site sequence. The sequences will be as follows, ABDC, BCAD, CDBA, and DACB, where A=buttock, B=abdomen, C=thigh, and D=back of upper arm. The injection site sequence assignment will be made at the time of Group randomization.

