#### Table 1: Schedule of Assessments – Group 1 (CAM2038 q1w) Campulation

a Subjects must voluntarily provide written informed consent prior to any study-related procedures being performed.

b Prior to treatment on Day 1, all Inclusion and none of the Exclusion criteria must be met.

c Vital signs (temperature, blood pressure, pulse rate, respiratory rate) will be measured pre-dose and 15 minutes' post-dose after each CAM2038 q1w administration and will be measured once at each non-dosing visit.

d ECG will be measured at the Screening and EOT visits, and pre-dose and 23 (±2) hours after the first CAM2038 q1w administration. ECGs will be measured at 1, 4, 6, 10, 24, 48, 72, 96 and 168 hours post-dose on doses 4 through 7.

e Assessment of serum sodium, bicarbonate, potassium, magnesium, calcium levels only.

 $^{\rm f}$  A serum pregnancy test will be performed at Screening and EOT visits. An "in-office" urine pregnancy test will be required prior to all doses of CAM2038 q1w (for women of childbearing potential) during days 1 through 50. An "in-office" urine pregnancy test will be required prior to all doses of CAM2038 q1w (for women of childbearing potential) for those women who continue in the extension phase will also be required.

g Any spontaneously reported AEs will be recorded after the subject signs the ICF. In addition, AEs will be elicited using a non-leading question each time the subject visits the clinic and once daily during inpatient stays.

Version: 5.0, 05 OCT 2016

Page 38 of 87

п5-15-549													 ΜΥΓΙ	DENT.	IAL
Study Period/Phase:	Screening			Tre	atment	Phase		Op	en-lab	el Sa	fety E	xtensi	on Pl	iase	
Treatment:				C	AM2038	8 q1w		CAM2038 q1w							FU
CAM2038 q1w Dose:			Doses	1 to 3		Da	oses 4 to 7	Doses 8 - 13							1
Day:	-21 to -1	D1	D2	D8	D15	D22, D29 D36,	D23-27, D30- 34, D37-41, D44-48	D50/ EOT	D57	D64	D71	D78	D85	D92/ EOT	D99 / FU
C-SSRS h	Х	Х	X	Х	Х	Х		X			X			X	
Injection Site Examination 		Х	X	Х	Х	Х	X	X	X	X	X	Х	X	X	
PK samples		X j		X j	Xj	Х	X k	X k						X	
cows 		Х	X	X	Х	Х		X						X	
sows 		Х	X	X	Х	Х		X						X	
UDS and Breath Alcohol Test	Х	Х	X	Х	Х	Х	X	X			X			X	
NRS for Pain m	Х	Х	X	Х	Х	Х	X	X	X	X	X	Х	X	X	
Randomization n		Х													
CAM2038 q1w SC injection 		X		X	Х	Х		X	X	X	X	X	X		

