#### Table 2: Schedule of Assessments – Group 2 (128 mg CAM2038 q4w) Page 2 (128 mg CAM2038 q4w)

a Subjects must voluntarily provide written informed consent prior to any study-related procedures being performed.

b Prior to treatment on Day 1, all Inclusion and none of the Exclusion criteria must be met.

c Vital signs (temperature, blood pressure, pulse rate, respiratory rate) will be measured pre-dose and 15 minutes post-dose after each CAM2038 q4w administration. Vital signs will also be measured at the Screening, Day 2 and EOT visits, and at each admission.

d ECG will be measured at the Screening and EOT visits, and pre-dose and 6 (±1) hours after each CAM2038 q4w administration. After dose 4, ECGs will be measured at 1, 4, 6, 10, 24, 72, 120, 168 (7 days), 336 (14 days) and 672 (28 days) hours post-dose.

e Assessment of serum sodium, bicarbonate, potassium, magnesium, calcium levels only.

f A serum pregnancy test will be performed at Screening and EOT visits. An "in-office" urine pregnancy test will be required prior to all doses of CAM2038 q4w (for women of childbearing potential) during days 1 through 113. An "in-office" urine pregnancy test will be required prior to all doses of CAM2038 q1w (for women of childbearing potential) for those women that continue to the extension phase.

Clinical Study Protocol Braeburn Pharmaceuticals HS-15-549 g Any spontaneously reported AEs will be recorded after the subject signs the ICF. In addition, AEs will be elicited using a non-leading question each time the subject visits the clinic and once daily during inpatient stays.

Study Period/Phase:	Screening	Treatment Phase											Open-label Safety Extension Phase							
Treatment:					12	28 mg	CAN	A2038	8 q4w				CAM2038 q1w							
CAM2038 q4w Dose:		1	Dose	1	Do	se 2	Do	se 3		D	ose 4									
Day:	-21 to -1	D1	D2	D8 D15 D22	D29	D31 D36 D43 D50	D57	D59 D64 D71 D78	D85	D86	D87, D88 D89, D90 D92, D95 D99, D106	D113/ EOT	D120	D127	D134	D141	D148	D155/ EOT	D162	
C-SSRS h	X	X	Х		Х		X		X			Х			X			X		
Injection Site Examination 		X	Х	X	X	X	X	Х	X	X	Х	Х	X	Х	X	X	X	X		
PK samples		Xj		хj	Xk	X k	X k	X k	X l	X	X m	Х						X		
cows n		X	Х		Х		X		X			Х						X		
sows n		X	Х		Х		X		X			Х						X		
UDS and breath alcohol test	X	X	Х	X	Х	Х	X	Х	X	Х	Х	Х			X			X		
NRS for Pain 	X	X	Х	X	Х	Х	X	Х	X	Х	X	Х	X	X	X	X	X	X		

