BMI=body mass index; BPN=buprenorphine; COWS=Clinical Opioid Withdrawal Scale; CRU=clinical research unit; C-SSRS=Columbia-Suicide Severity Rating Scale; D=day; ECG=electrocardiogram; EOT=End of Treatment; NRS=numerical rating scale; PK=pharmacokinetic; SC=subcutaneous; SOWS=Subjective Opioid Withdrawal Scale; UDS=urine drug screen.

Study Period/Phase:	Screening		Treatment Phase												
Treatment:		CI	DDM						160 1	mg CAM20	38 q4w				FU
		SL	BLN		Dose 1			ose 2		Dose 3			Dose 4		1
Day:	-21 to -1	D1 - D6	D7	D8	D9	D15 D22 D29	D36	D38, D43, D50, D57	D64	D66, D71, D78, D85	D92	D93	D94, D95, D96, D97, D99, D102, D106, D113	D120/ EOT	D127
Informed Consent a	Х														
Eligibility Criteria Review b	Х	Х													]
Medical, Psychosocial and Medication History	X														
Substance Use and Treatment History	Х														
Complete Physical Examination	Х													Х	
Weight, BMI	Х													Х	
Height	Х														
Vital Signs C	Х	Х	Х	X	Х	Х	X	Х	Х	X	Х	Х	X	Х	
ECG d	Х	Х	Х	X			X		X		X	Х	Х	Х	
Biochemistry, Hematology, Urinalysis, and Coagulation Profile	X	X e		X			xf		xf		xf			Х	
Pregnancy Test g	Х	Х		X			X		Х		X			Х	
Adverse Events h	Х	Х	Х	Х	Х	Х	Х	Х	Х	Х	Х	Х	X	Х	Х

a Subjects must voluntarily provide written informed consent prior to any study-related procedures being performed.

b Prior to treatment on Day 1, all Inclusion and none of the Exclusion criteria must be met.

c Vital signs (temperature, blood pressure, pulse rate, respiratory rate) will be measured pre-dose and 15 minutes post-dose after the SL BPN dose on Day 1 and after each CAM2038 q4w administration. Vital signs will also be measured at the Screening, Day 8 discharge, Day 9 and EOT visits, and at each admission.

d ECG will be measured at the Screening and EOT visits, at pre-dose and 1 hour after SL BPN administration on Day 1, and pre-dose and 6 (±1) hours after each CAM2038 q4w administration. After CAM2038 dose 4, ECGs will be measured at 1, 4, 6, 10, 24, 72, 120, 168 (7 days), 336 (14 days) and 672 (28 days) hours post-dose.

e Day 1 only.

f Assessment of serum sodium, bicarbonate, potassium, magnesium, calcium levels only.

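### SAP 6.1 does not require a pre-dose baseline, so Day 1 post-dose ECGs (Group 2) and vital signs (Groups 1 and 2) become the baseline or are averaged into it

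*SAP*

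**What the plan says.** SAP 6.1 gives the general rule: "the last observed measurement on the date of randomization will be considered the baseline measurement". Its next sentence says that where there are several observations, "the baseline will be defined as average of the observations obtained during the baseline phase". SAP 4.3 names four phases (Screening, Treatment, open-label safety extension, Follow-up), and none is a baseline phase.

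Protocol 9.3 fixes the date: "On Day 1, before the first dose of CAM2038, subjects will be randomized into Group 1" or Group 2. Randomization and first injection therefore share a calendar day.

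The schedules in Protocol Section 10 place these readings around the first dose:

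- Group 2 ECG (Table 2, footnote d): "pre-dose and 6 (±1) hours after each CAM2038 q4w administration". The grid has no Day 2 ECG.
- Group 2 vital signs (Table 2, footnote c): "will be measured pre-dose and 15 minutes post-dose after each CAM2038 q4w administration".
- Group 1 vital signs (Table 1, footnote c): pre-dose and 15 minutes "post-dose after each CAM2038 q1w administration and will be measured once at each non-dosing visit".
- Group 1 ECG (Table 1, footnote d): "pre-dose and 23 (±2) hours after the first CAM2038 q1w administration", so the first post-dose ECG falls on Day 2.
- Group 3 ECG (Table 3, footnote d): "at pre-dose and 1 hour after SL BPN administration on Day 1". Group 3 vital signs are also taken before and 15 minutes after that dose.

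Protocol 12.3.3 calls for change-from-baseline statistics for ECG and vital signs. SAP 11.6 and 11.8 report those changes without a baseline rule of their own. Only laboratory tests have one (SAP 11.5). Group 3 is not randomized (Protocol 7.1, SAP 4.2), yet SAP 6.1 names only the date of randomization.

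**The concern.** A change from baseline measures the effect of treatment only if the baseline comes before treatment. Here the date rule admits readings taken after the first injection, and for two measures the last reading of that day is scheduled after it.

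In Group 2 this bears on the switch from sublingual buprenorphine to the depot. With no Day 2 ECG, the 6-hour reading is the only scheduled post-dose ECG before Day 8 at the earliest. Protocol 10.7 says that frequent ECGs are included to monitor possible QTc prolongation. If the 6-hour reading serves as the baseline, the change tables cannot show what happened between the pre-dose reading and 6 hours, and every later change is measured from a point already on treatment. The 15-minute vital signs in Groups 1 and 2 raise the same problem.

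**Working it through.** The plan states no figure to reproduce. The check applies the SAP 6.1 rule to the scheduled Day 1 times and works out the effect by algebra.

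**Step 1: which Day 1 reading is last?**

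| Measure | Day 1 readings | Last on Day 1 |
|---|---|---|
| Group 1 ECG | pre-dose only (next at 21 to 25 h) | pre-dose: not affected |
| Group 1 vital signs | pre-dose, 15 min | post-dose |
| Group 2 ECG | pre-dose, 5 to 7 h | post-dose |
| Group 2 vital signs | pre-dose, 15 min | post-dose |

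COWS and SOWS are done pre-dose on dosing days and are not affected. Nor are Group 1 and 2 laboratory tests: SAP 11.5 takes the last value on or before randomization, randomization precedes dosing, and no Day 1 post-dose laboratory sample is scheduled.

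**Step 2: effect on the reported change.** For one subject let P be the Day 1 pre-dose reading, H the Day 1 post-dose reading, X a later reading, and e = H − P. Let w be the weight of H in the baseline, so baseline = P + w·e. The first sentence of 6.1 gives w = 1. Averaging the two Day 1 readings gives w = 1/2.

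- Reported Day 1 post-dose change: H − (P + w·e) = (1 − w)·e, which is 0 for w = 1 and e/2 for w = 1/2.
- Reported later change: X − (P + w·e) = (X − P) − w·e.

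No mean or standard deviation is assumed.

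**Step 3: Day 1 against the SAP 11.8 categories (<30, 30 to <60, ≥60 msec).** A true 6-hour rise of 60 msec is reported as 0 (w = 1) or 30 msec (w = 1/2). To be counted as ≥30 msec, the true rise must be 30/(1/2) = 60 msec under averaging; to be counted as ≥60 msec, it must be 60/(1/2) = 120 msec. With w = 1 no rise is ever counted. These figures illustrate the rule and are not expected values.

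**Step 4: later visits.** A later change is counted as ≥30 msec only if the true change from pre-dose reaches 30 + w·e, and as ≥60 msec only if it reaches 60 + w·e. The documents give no e, so the range below is an assumption.

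| e (msec, assumed) | 30-msec cut-off, w = 1 | 30-msec cut-off, w = 1/2 | 60-msec cut-off, w = 1 | 60-msec cut-off, w = 1/2 |
|---|---|---|---|---|
| −10 | 20 | 25 | 50 | 55 |
| −5 | 25 | 27.5 | 55 | 57.5 |
| 0 | 30 | 30 | 60 | 60 |
| 5 | 35 | 32.5 | 65 | 62.5 |
| 10 | 40 | 35 | 70 | 65 |

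A rise on Day 1 makes later prolongation look smaller, and a fall makes it look larger. The same formula applies to the vital-sign changes in SAP 11.6.

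**Step 5: how many subjects.** Group 2 has about 16 planned subjects with the ECG reading. Groups 1 and 2 together have up to about 24 + 16 = 40 with the vital-sign reading.

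**Step 6: Group 3.** SAP 11.4 dates treatment-emergent events in Group 3 from the first SL BPN dose, but SAP 6.1 does not use that anchor. Substituting Day 1 for randomization would bring in the 1-hour ECG and the 15-minute vital signs. Substituting Day 8, the first CAM2038 day, would bring in that day's post-dose readings. Either anchor needs the pre-dose condition.

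**The case against.** The strongest reply is that the second sentence of 6.1 rescues the rule. If a baseline phase has its ordinary pre-treatment meaning, the post-dose reading is outside it (w = 0), and an experienced programmer would use the pre-dose value anyway. That reading is reasonable, but the SAP does not state it. The first sentence works by date alone, and the averaging sentence may have been written with the daily pain diary in mind without being limited to it. What stands is that it would be too strong to say the SAP simply makes the post-dose reading the baseline: that relies on the first sentence alone.

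Other parts of the reply also stand. Buprenorphine is taken up to Day −1 and the depot is described as having minimal initial burst (Protocol 7.1, 5.1), so e may be close to zero, particularly at 15 minutes. SAP 11.8 tabulates changes by visit and does not say how two Day 1 readings are shown, so a separate 6-hour change is an inference about the output; the shift at later visits does not depend on it. Formal safety comparisons are post hoc (SAP 11.0).

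For Group 3, a reader might infer that no baseline can be derived at all. The documents do not support that: SAP 11.4 supplies a usable date and pre-dose readings are scheduled. A pre-CAM2038 baseline is also plausible, because Day 9 is meant to assess the transition from SL BPN.

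**Conclusion.** The point holds in this form. SAP 6.1 lets on-treatment readings act as the baseline, or as half of it, for the Group 2 ECG and the Group 1 and 2 vital signs. No other section corrects this. A Day 1 post-dose change is then reported at zero or half size, and later changes are off by e or e/2 in either direction. Over an assumed e of −10 to 10 msec, the QTc cut-offs move by at most 10 msec (last value) or 5 msec (average). At e = 0 they do not move.

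Two stronger readings are not supported. One is that the plan hides QTc prolongation: neither the size nor the sign of e is given, and the absolute QTc categories and the concentration–QT plots do not use baseline. The other is that the discontinuation criterion in Protocol 10.5.5 is affected: SAP 6.1 governs the analysis, and the documents do not say that sites use it.

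PK results are untouched. This should be fixed, but it does not threaten the primary objectives.

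**What to change.** In SAP 6.1, define baseline for ECG and vital signs as the last non-missing value before the date and time of the first study dose, using the scheduled time-point label if the clock time is missing. State that Day 1 post-dose readings are post-baseline. Limit averaging to pre-dose replicates. Give the pain NRS its own baseline, an average of diary scores before the first dose, with its window stated.

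For Group 3, replace randomization with a stated anchor. It can be the reading before the first SL BPN dose, in line with SAP 11.4, or the reading before the first CAM2038 dose if change from SL BPN is what is meant. Use the pre-dose reading in either case. SAP 11.5 needs the same anchor for Group 3 only. The adverse-event dating text that still says randomization can be tidied at the same time, but that is a separate wording matter.

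The cost is SAP wording and programming, because the pre-dose readings are already scheduled. SAP 9.3 lets Groups 1 and 2 be locked and reported before Group 3, so the revision should be made before that lock, so that the baseline is not chosen after the data are seen.
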